1. LIST OF ABBREVIATIONS

Table 1: List of Abbreviations

Term/Abbreviation	Definition
10MWT	10-meter walk test
6MWD	6-minute walk distance
AE	adverse event
AT2221	INN: miglustat; N -butyl-deoxynojirimycin; iminosugar that is used as an enzyme stabilizer to ATB200 (a recombinant human acid α -glucosidase)
ATB200	INN: cipaglucosidase alfa; recombinant human acid α -glucosidase (rhGAA) enzyme with optimized carbohydrate structures, including mannose 6-phosphate (M6P), to enhance uptake and delivery of active ATB200 to lysosomes
CI	confidence interval
CK	creatinine kinase
CSR	clinical study report
DBL	database lock
ECG	electrocardiogram
eCRF	electronic case report form
ERT	enzyme replacement therapy
FSS	Fatigue Severity Scale
FVC	forced vital capacity
GAA	human acid α -glucosidase, may be specified as either GAA enzyme activity or GAA protein
GSGC	Gait, Stairs, Gowers', Chair
Hex4	hexose tetrasaccharide
IAR	infusion-associated reaction
iCSR	interim clinical study report
IMG	immunogenicity
IV	intravenous
MEP	maximum expiratory pressure
MIP	maximum inspiratory pressure
MMT	manual muscle test
PD	pharmacodynamic or pharmacodynamics
PDLC	pre-defined limits of change

Table 1: List of Abbreviations (Continued)

Term/Abbreviation	Definition
PFT	pulmonary function test
PGIC	Physician's Global Impression of Change
PK	pharmacokinetic or pharmacokinetics
PRO	patient-reported outcome
PROMIS®	Patient-reported Outcomes Measurement Information System
PT	preferred term
QMT	quantitative muscle test
rhGAA	recombinant human acid α-glucosidase
RHS	Rotterdam Handicap Scale
R-PAct	Rasch-built Pompe-specific Activity
SAP	statistical analysis plan
SGIC	Subject's Global Impression of Change
SNIP	sniff nasal inspiratory pressure
SOC	system organ class
TEAE	treatment-emergent adverse event
TESAE	treatment-emergent serious adverse event
TUG	Timed Up and Go

2. INTRODUCTION

This statistical analysis plan (SAP) is based on Amendment 8 to Protocol ATB200-02 dated 10 January 2019. The purpose of this SAP is to describe the planned data analyses and outputs to be included in the final clinical study report (CSR) to close out the study. Most of the subjects in Study ATB200-02 are expected to transition to commercial products while a few will transition to the sponsor's expanded access program (EAP) Study ATB200-11. The expected database lock (DBL) date for the final CSR is 24 July 2024.

The study design consists of 4 stages as described in Section 5 (and represented in Table 2), and the stages are as follows:

- Stage 1 involves the administration of a single-ascending dose (SAD) of ATB200 (also referred to as cipaglucosidase alfa) alone, with focus on safety, tolerability, and pharmacokinetic (PK) assessments.
- Stage 2 involves the co-administration of multiple-ascending doses (MAD) of ATB200/AT2221 (also referred to as cipaglucosidase alfa/miglustat), with a focus on safety (including pharmacodynamics [PD]) and PK assessments.
- Stages 3 and 4 involve a fixed dosing regimen of ATB200/AT2221 co-administration to support the proof of concept and the long-term extension phase of the study (with long-term efficacy and safety assessments).

The ATB200-02 study data have been reported previously in 2 interim clinical study reports and 1 addendum. The first interim clinical study report (iCSR-1), dated 15 December 2020, was based on the data cutoff date of 19 June 2020 and focused mainly on the analyses of the study data during Stages 1 and 2, including the complete analysis of the PK data, as well as the safety and PD data collected prior to the co-administration of the fixed dosing regimen of 20 mg/kg cipaglucosidase alfa + 260 mg miglustat. An addendum to iCSR-1, dated 11 May 2021, was based on the data cutoff date of 13 November 2020. The second interim clinical study report (iCSR-2), dated 31 August 2022, focused on the analysis of long-term efficacy, PD, immunogenicity (IMG), and safety data collected during Stage 2 Period 5 through Stages 3 and 4 that were available at the time of the data cutoff date of 13 December 2021.

As this is the final CSR, the plan is to report all data for the study using summary tables and/or listings. The current SAP describes the analyses of long-term data on safety, efficacy, and PD collected from Stage 2 Period 5 through the DBL date. No new PK samples are available since iCSR-1, and therefore PK analyses from iCSR-1 will be referenced or copied into the final CSR. Similarly, safety and PD analyses for Stages 1 and 2 reported in iCSR-1 will be copied into the final CSR, unless the underlying data have changed.

This SAP has been developed in accordance with Good Clinical Practice (GCP), International Conference on Harmonisation (ICH) guideline E9 (Statistical Principles for Clinical Trials), and Amicus standard operating procedure (SOP) ATCRA-SOP-AT-008. All decisions regarding the final analyses for the CSR, as defined in this SAP document, will be made prior to the expected study DBL date.

The SAP may evolve over time to incorporate important changes, including changes that reflect feedback and comments from regulatory interaction. However, the final SAP will be finalized

and placed on file before the DBL date. The analyses and statistical methods specified in this SAP supersede those described in the study protocol.

3. STUDY OBJECTIVES

For ease of presentation, the study objectives are presented by stage.

3.1. Objectives for Stage 1

Primary objectives for Stage 1 are:

- To evaluate the safety and tolerability of single-ascending doses of intravenously (IV) infused ATB200
- To characterize the PK of single-ascending doses of IV infused ATB200

An exploratory objective for Stage 1 is:

- To evaluate PD markers (urine hexose tetrasaccharide [Hex4] and serum creatine kinase [CK])

3.2. Objectives for Stage 2

Primary objectives for Stage 2 are:

- To evaluate the safety and tolerability of single doses of IV infused ATB200 as a fixed dose, co-administered with ascending oral doses of AT2221
- To characterize the single- and multiple-dose plasma total human acid α -glucosidase (GAA) protein PK of IV infused 20 mg/kg ATB200 when co-administered with oral 130 mg or 260 mg AT2221 in enzyme replacement therapy (ERT)-experienced subjects with late-onset Pompe disease (LOPD)
- To characterize the single- and multiple-dose plasma GAA activity PD of IV infused 20 mg/kg ATB200 when co-administered with oral 130 mg or 260 mg AT2221 in ERT-experienced subjects with LOPD
- To characterize the plasma miglustat PK of single and multiple oral doses of 130 mg or 260 mg AT2221 when co-administered with IV infused ATB200 in ERT-experienced subjects with LOPD

An exploratory objective for Stage 2 is:

- To evaluate PD markers (urinary Hex4 and serum CK)

3.3. Objectives for Stages 3 and 4

Primary objectives for Stages 3 and 4 are:

- To evaluate the long-term safety and tolerability of 20 mg/kg of IV infused ATB200 as a fixed dose co-administered with oral 260 mg AT2221 in all subjects from Stage 3
- To evaluate the long-term efficacy of 20 mg/kg of IV infused ATB200 as a fixed dose co-administered with oral 260 mg AT2221 in all subjects from Stage 3
- To characterize the single- and multiple-dose plasma total GAA protein PK of IV infused 20 mg/kg ATB200 when co-administered with oral 260 mg AT2221 in ERT-naïve subjects with LOPD

- To characterize the single- and multiple-dose plasma GAA activity PD of IV infused 20 mg/kg ATB200 when co-administered with oral 260 mg AT2221 in ERT-naïve subjects with LOPD
- To characterize the plasma miglustat PK of single and multiple oral doses of 260 mg AT2221 when co-administered with IV infused ATB200 in ERT-naïve subjects with LOPD

Exploratory objectives for Stages 3 and 4 are:

- To evaluate anti-rhGAA (recombinant human acid α -glucosidase) antibodies (total and neutralizing)
- To evaluate cross-reactivity of anti-rhGAA antibodies to alglucosidase alfa
- To evaluate pro-inflammatory cytokines and other biomarkers of immune system activation
- To evaluate PD markers (urinary Hex4 and serum CK)
- To evaluate the impact of anti-rhGAA antibodies and neutralizing antibodies on plasma GAA total protein exposures, safety (adverse events [AEs] and infusion-associated reactions [IARs]), and efficacy (6-minute walk distance [6MWD] and pulmonary function tests [PFTs])

4. ENDPOINTS

4.1. Pharmacokinetic Parameters

Descriptions and definitions of the plasma PK parameters for signature peptides T09 and T50 from total GAA protein concentrations, GAA activity levels, and miglustat concentrations are provided in Section 12.4.4.1 of Protocol ATB200-02.

Noncompartmental analyses for ATB200 and AT2221 include the following:

- Stage 1 PK (derived signature peptides T09 and T50 from total GAA protein concentrations and GAA activity levels) parameters in plasma
- Stage 2 (ERT-experienced) PK (derived signature peptides T09 and T50 from total GAA protein concentrations, GAA activity levels, and miglustat concentrations) parameters in plasma
- Stage 3 (ERT-naïve) PK (derived signature peptides T09 and T50 from total GAA protein concentrations, GAA activity levels, and miglustat concentrations) parameters in plasma
- Stage 4 (ERT-experienced) long-term sparse plasma PK sampling for signature peptides T09 and T50 from total GAA protein and miglustat concentrations population PK analysis

4.2. Safety Variables

Safety analyses will be performed for the following endpoints:

- Study drug exposure and compliance
- Identification and counts of treatment-emergent adverse events (TEAEs), and treatment-emergent serious adverse events (TESAEs), including IARs
- Change from baseline in 12-lead electrocardiogram (ECG)
- Change from baseline in clinical safety laboratory evaluations, including serum chemistry, hematology, and urinalysis
- Change from baseline in physical examinations (PEs)
- Change from baseline in vital signs

4.3. Pharmacodynamic Variables

PD analyses will be performed for the following endpoints:

- Change from baseline in Hex4
- Change from baseline in CK

4.4. Efficacy Variables

Efficacy analyses will be performed for the following endpoints:

Functional measurements for ambulatory subjects:

- Change and percent change from baseline in Gowers' maneuver, 4-stair climb, 6MWD, percent predicted 6MWD, 10-meter walk test (10MWT), total score of Gait, Stairs, Gowers', Chair (GSGC), Timed Up and Go (TUG), muscle strength tests (manual muscle tests [MMT] using Medical Research Council [MRC] scale and quantitative muscle test [QMT] based on hand-held dynamometer) for both upper and lower limbs
- Change and percent change from baseline in PFTs including forced vital capacity (FVC), maximum inspiratory pressure (MIP), maximum expiratory pressure (MEP), and sniff nasal inspiratory pressure (SNIP) for subjects without invasive ventilatory support

Functional measurements for non-ambulatory subjects:

- Change and percent change from baseline in MMT and QMT for upper limbs only
- Change and percent change from baseline in PFTs (FVC, MIP, MEP, and SNIP [for subjects without invasive ventilatory support])

Patient-reported Outcomes (PROs):

- Change and percent change from baseline in the total score of Fatigue Severity Scale (FSS), Rotterdam Handicap Scale (RHS), Rasch-built Pompe-specific Activity (R-PAct) scale, and Patient-reported Outcomes Measurement Information System (PROMIS®) scale

Global Impression of Change:

- Physician's Global Impression of Change (PGIC) and Subject's Global Impression of Change (SGIC)

Note: Further descriptions of the efficacy variables are provided in [Appendix 1](#).

4.5. Immunogenicity Variables

Details of IMG variables are described in a separate Modeling and Simulation Plan.

5. STUDY DESIGN

5.1. Summary of Study Design

This is an open-label, fixed-sequence, single- and multiple-ascending dose, first-in-human (FIH) study to evaluate the safety, tolerability, PK, PD, and efficacy of intravenous ATB200 alone and when co-administered with oral AT2221. The study was conducted in 4 stages and enrolled 4 cohorts as shown in [Table 2](#).

The 4 cohorts in the study are as follows:

- Cohort 1: this cohort was planned to enroll 11 ERT-experienced ambulatory subjects defined as adults with Pompe disease who have been on ERT for 2 to 6 years prior to enrollment and are able to walk at least 200 meters in the 6-minute walk test (6MWT).
- Cohort 2: this cohort was planned to enroll 4 to 6 ERT-experienced non-ambulatory subjects defined as adults with Pompe disease who are wheelchair-bound and unable to walk unassisted and have been on ERT for \geq 2 years prior to enrollment.
- Cohort 3: this cohort was planned to enroll 5 ERT-naïve ambulatory subjects defined as adults with Pompe disease who have never received treatment with ERT and who are able to walk at least 200 meters in the 6MWT.
- Cohort 4: this cohort was planned to enroll 6 to 8 ERT-experienced ambulatory subjects defined as adults with Pompe disease who have been on ERT for at least 7 years prior to enrollment and are able to walk at least 75 meters in the 6MWT. This cohort was added after Amendment 5 to Protocol ATB200-02.

The 4 study stages are as follows:

- Stage 1 is a 3-period, fixed-sequence, single-ascending dose PK study of ATB200 alone. Safety, tolerability, and PK were evaluated following sequential single-ascending doses of 5 mg/kg, 10 mg/kg, and 20 mg/kg of IV infused ATB200 administered 2 weeks apart. Only subjects in Cohort 1 participated in Stage 1.
- Stage 2 is a 2-period, fixed-sequence, single- and multiple-dose PK study of 20 mg/kg ATB200 co-administered with multiple-ascending doses of AT2221. In Stage 2, safety, tolerability, and PK were evaluated following single- and multiple-ascending dose combinations: 20 mg/kg of IV infused ATB200 co-administered with 130 mg of AT2221 administered orally every 14 days (\pm 3 days) for 3 doses, followed by 20 mg/kg of IV infused ATB200 co-administered with 260 mg of AT2221 administered orally for 3 doses. Only subjects in Cohort 1 participated in Stage 2.
- Stage 3: Cohort 1 subjects who completed Stages 1 and 2 entered into an extension stage of the study, during which they continued on extended treatment with 20 mg/kg of IV infused ATB200 co-administered with 260 mg of AT2221 administered orally. Additionally, during Stage 3, three new cohorts – Cohorts 2, 3, and 4, were enrolled. Subjects from Cohorts 2, 3, and 4 were treated with 20 mg/kg of IV infused ATB200 co-administered with 260 mg of AT2221 administered orally every 2 weeks. The

duration of Stage 3 was 2 years, and all subjects were evaluated for safety, tolerability, PD, and efficacy. In addition, disease-relevant functional assessments were performed at regular intervals. Key messages from Stage 3 will help support the proof-of-concept based on the efficacy endpoints.

- The Stage 4 treatment period began at the end of Stage 3 and will continue as a long-term extension to provide additional safety and efficacy data until subject withdrawal, regulatory approval, or marketing authorization and/or commercialization in the participating subject's country, or study termination by the sponsor, Amicus Therapeutics (Amicus).

Table 2: Treatment Assignment by Cohort and Stage

Cohorts	Stage 1 (6 weeks)			Stage 2 (12 weeks)		Stage 3 (2 years)	Stage 4 (Until Approval)
	Period 1 Single-dose	Period 2 Single-dose	Period 3 Single-dose	Period 4 3 Multiple Doses Co-administration	Period 5 3 Multiple Doses Co-administration	Multiple Dose, 24 months, Extension Co-administration	Multiple Dose, Long-term, Extension Co-administration
Cohort 1 (n = 11)	5 mg/kg ATB200	10 mg/kg ATB200	20 mg/kg ATB200	20 mg/kg ATB200 + 130 mg AT2221	20 mg/kg ATB200 + 260 mg AT2221	20 mg/kg ATB200 + 260 mg AT2221	20 mg/kg ATB200 + 260 mg AT2221
Cohort 2 (n = 4-6)	NA			20 mg/kg ATB200 + 260 mg AT2221		20 mg/kg ATB200 + 260 mg AT2221	
Cohort 3 (n = 5)	NA			20 mg/kg ATB200 + 260 mg AT2221		20 mg/kg ATB200 + 260 mg AT2221	
Cohort 4 (n = 6-8)	NA			20 mg/kg ATB200 + 260 mg AT2221		20 mg/kg ATB200 + 260 mg AT2221	

Abbreviations: ATB200 = cipaglucosidase alfa; AT2221 = miglustat; NA = not applicable

Note: At least 1 of the 2 sentinel subjects will complete Stage 2, Period 5 and the safety data will be reviewed by the Safety Steering Committee (SSC) before dosing any newly enrolled subjects from Cohorts 2 and 3. The first 2 subjects from Cohorts 2 and 3 will also serve as sentinel subjects for their respective cohorts.

For details of assessments to be performed at each study visit, please refer to Table 9 through Table 15 in Protocol ATB200-02.

5.2. Definition of Study Medications

Study drugs for Stages 1, 2, 3, and 4 are defined in [Table 2](#) above. The study drug that is being investigated is cipaglucosidase alfa co-administered with miglustat, which is also denoted as cipaglucosidase alfa/miglustat (or ATB200/AT2221). Where necessary, these denotations will be used interchangeably in this document.

- Cipaglucosidase alfa (or ATB200): a recombinant human acid α -glucosidase (rhGAA) enzyme with optimized carbohydrate structures that functions as an ERT. This is administered intravenously.
- Miglustat (AT2221): *N*-butyl-deoxynojirimycin. This is an iminosugar that functions as a selective enzyme stabilizer of rhGAA. This is administered orally.

5.3. Sample Size Considerations

5.3.1. Sample Size Justification

No formal sample size calculation was performed, as this began as a FIH study in a single cohort using a sentinel dosing scheme, and no hypothesis test was specified.

The plan was to increase the sample size as the study expanded to include additional cohorts. A sample size of between 18 to 34 subjects across 4 cohorts was considered adequate for the purposes of evaluating safety and tolerability as well as providing preliminary efficacy data in this study.

5.3.2. Sample Size Re-estimation

No formal sample size re-estimation was planned for this study.

5.4. Randomization and Stratification

Randomization and stratification are not applicable to this study, as subjects received open-label treatment.

5.5. Clinical Assessments

Study assessments were to be performed in accordance with the Schedule of Assessments as provided in Table 9 through Table 15 in Protocol ATB200-02.

5.6. Interim Analyses

No formal interim analysis (ie, one that involves some strategy for early stopping or adjustment of the testing procedure to maintain an overall type I error rate) is planned for this study.

However, the protocol allowed informal interim analyses to be performed in the study as needed.

As of 31 December 2023, there have been approximately 11 different data cuts for informal interim analyses under separate SAPs to support publications, conference presentations, and regulatory submissions, including 2 interim CSRs. The DBL for this final CSR is planned for 24 July 2024.

5.7. Multicenter Studies

Because a small number of subjects were expected at each center, data from all centers were to be pooled for analysis.

6. GENERAL CONSIDERATIONS FOR DATA ANALYSIS

6.1. Analysis Populations

The number of subjects enrolled and the number and percentage of subjects in each analysis population will be summarized by cohort and the total.

A listing of subjects in the analysis populations will be provided and it will include the study stage and cohort. There will be no separate listings by stage.

6.1.1. All Enrolled Subjects

The All Enrolled Subjects population includes all subjects who entered the study, completed the study entry procedures, and satisfied the eligibility criteria for the study, based on the inclusion and exclusion criteria. This includes:

- All subjects enrolled into Cohort 1 (ie, entered any of the 4 study stages: Stage 1, Stage 2, Stage 3, and Stage 4).
- All subjects enrolled into Cohorts 2, 3, and 4.

The All Enrolled Subjects population will be used for subjects' accounting purposes, summary of demographic and baseline characteristics, protocol deviations, and for some data listings.

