12.4. Data Analysis Considerations

12.4.1. Analysis Populations

- Safety Population: this includes all enrolled subjects who have been exposed to at least 1 dose of study treatment (ATB200 and/or AT2221).
 - The Safety population will be used in the analysis of all safety parameters (including AEs, vital signs, laboratory assessments, and biomarkers).
- PK Analysis Population: includes enrolled subjects who have been exposed to at least 1 dose of study treatment (ATB200 and/or AT2221) and have completed at least 1 PK period.
 - The PK population will be used for PK analyses.
- Intent-to-Treat Population: includes all enrolled subjects.
- Other populations may be defined in the SAP.

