6.1.2. Safety Population

The Safety population consists of all enrolled subjects who were exposed to at least 1 dose of study medication.

- For Stage 1, this includes all Cohort 1 subjects who were administered at least one IV infusion of ATB200 as a single agent during Stage 1.
- For Stage 2, this includes all Cohort 1 subjects who entered Stage 2 and received at least one IV infusion of 20 mg/kg ATB200 co-administered with either 130 mg or 260 mg of AT2221.
- For Stages 3 and 4, this includes all Cohort 1 subjects who entered Stage 2 Period 5 and received at least one dose of the fixed therapy 20 mg/kg ATB200 + 260 mg AT2221, as well as all the subjects who were later enrolled into Cohorts 2, 3, and 4 in Stage 3 and received at least one dose of the study medication.

Safety analyses for Stages 1 and 2 were completed and reported in iCSR-1, and they will not be repeated in this SAP unless there has been a change in the underlying data. The plan is to copy the pertinent summaries from the iCSR-1 into the final CSR. This SAP describes the analysis of safety data covered in the last bulleted item, following the co-administration of the fixed therapy 20 mg/kg ATB200 + 260 mg AT2221. All safety analyses will be conducted on the Safety population, unless otherwise specified.

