6.1.3. Efficacy Population

The Efficacy population consists of all enrolled subjects who took at least 1 dose of the study medication (20 mg/kg ATB200 + 260 mg AT2221 co-administration) in Stage 3 and had both a baseline and at least 1 post-baseline assessment for any efficacy endpoint as listed in Section 4.4

(including assessments on motor function tests, muscle strength tests, PFTs, PROs, and Global Impression of Change). That is:

- For Cohort 1, this includes all subjects who entered Stage 2 Period 5 and received at least 1 dose of the 20 mg/kg ATB200 + 260 mg AT2221 co-administration and had both a baseline and at least 1 post-baseline assessment for any efficacy endpoint.
- For Cohorts 2, 3, and 4, this includes all subjects who received at least 1 dose of the 20 mg/kg ATB200 + 260 mg AT2221 co-administration and had both a baseline and at least 1 post-baseline assessment for any efficacy endpoint.

All efficacy analyses will be based on this population, unless otherwise specified.

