7.5. Listing of Subjects' Inclusion and Exclusion Criteria

A listing of subjects' inclusion and exclusion criteria will be provided showing which specific eligibility criteria were met/not met.

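### SAP 6.1.1 makes eligibility part of being enrolled, so a literal reading would drop a dosed but ineligible subject from the safety and efficacy summaries, against the SAP's own bullets

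*SAP*

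**What the plan says.** The lead sentence of SAP 6.1.1 admits subjects who entered the study, "completed the study entry procedures, and satisfied the eligibility criteria for the study". Two bullets follow: "All subjects enrolled into Cohort 1 (ie, entered any of the 4 study stages: Stage 1, Stage 2, Stage 3, and Stage 4" and "All subjects enrolled into Cohorts 2, 3, and 4". SAP 7.1, 7.3 and 7.4 use this population for disposition, important protocol deviations, and demographic and baseline characteristics.

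The next two populations are built on the same word. In SAP 6.1.2, "The Safety population consists of all enrolled subjects who were exposed to at least 1 dose of study medication". In SAP 6.1.3, "The Efficacy population consists of all enrolled subjects who took at least 1 dose of the study medication", with a further requirement for a baseline and a post-baseline value. SAP 10 puts all safety evaluations on the Safety population, and SAP 9.4 puts all efficacy analyses on the Efficacy population.

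SAP 7.5 plans a listing "showing which specific eligibility criteria were met/not met".

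Protocol 12.4.1 has no eligibility condition: "Intent-to-Treat Population: includes all enrolled subjects". SAP Section 2 says that the SAP overrides the protocol on analysis methods. SAP Table 11 records the move from ITT to All Enrolled Subjects and gives two reasons, clarity and the lack of randomisation. It does not mention an added eligibility condition.

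**The concern.** Safety and tolerability is a primary objective in both documents, and a safety set should depend on exposure alone. If being enrolled requires having satisfied the entry criteria, a subject found after dosing to have had, say, an FVC or walk distance out of range is not enrolled. That subject then fails the first condition of both Safety and Efficacy. The adverse events, infusion reactions and exposure of that subject would be missing from the summaries, and efficacy would be summarised on a set selected by eligibility. The table of important deviations would be produced on a set from which eligibility violators had been removed.

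The cohorts are small, so a single subject matters. Stage 3 lasts two years with dosing every two weeks. A subject who completes it contributes about 104 / 2 = 52 infusions from that stage alone.

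**Working it through.** There is no sample size, power or alpha figure to reproduce: SAP 5.3.1 and Protocol 12.3 state that no formal calculation was done. The check compares the definitions, then scales the effect of one subject.

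**Step 1. Lead sentences against bullets.**

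| SAP section | Lead sentence | Bullets beneath it |
|---|---|---|
| 6.1.1 All Enrolled | Entered, completed entry procedures and met eligibility | Cohort 1: glossed as having entered any stage, no eligibility test. Cohorts 2 to 4: says only enrolled |
| 6.1.2 Safety | Enrolled and dosed | Cohort 1: every subject dosed in the stage concerned. Cohorts 2 to 4: later enrolled and dosed |
| 6.1.3 Efficacy | Enrolled, dosed, baseline and post-baseline value | All cohorts: dosed, with baseline and post-baseline value; the word enrolled is absent |
| 6.1.4 PK | Exposed and completed a PK period; the word enrolled is absent | None |

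**Step 2. Follow the literal chain.** Take a subject who was dosed but violated a criterion. The lead sentence of 6.1.1 puts the subject outside All Enrolled. The lead sentences of 6.1.2 and 6.1.3 then put the subject outside Safety and Efficacy. The disposition, deviation, safety and efficacy summaries lose the subject. The PK definition does not, so the same person could be in the PK population and not in Safety.

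**Step 3. Follow the bullets.** In Cohort 1 the subject entered a stage and was dosed, so is in All Enrolled and in Safety. For Efficacy, any cohort, the subject is in if the assessments exist. For Safety in Cohorts 2 to 4 the answer depends on what enrolled means, which leads back to the lead sentence of 6.1.1. The conflict is sharpest there.

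**Step 4. Other sections.** SAP 7.3 summarises important deviations on All Enrolled Subjects. On the literal reading an eligibility violation could not appear in that table. Protocol 15.3 and 15.7 treat deviations from the entry criteria as a recognised category, so the case is foreseeable even though it is not permitted.

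**Step 5. Scale.** One subject as a share is 1/n. Cohort sizes and the overall range are from Protocol 9.1.

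- Cohort 1 (10 to 12): 1/12 = 8.3% to 1/10 = 10.0%; at the n = 11 in SAP Table 2, 9.1%
- Cohort 2 (4 to 6): 1/6 = 16.7% to 1/4 = 25.0%
- Cohort 3 (5): 1/5 = 20.0%
- Cohort 4 (6 to 8): 1/8 = 12.5% to 1/6 = 16.7%
- Whole study (18 to 34): 1/34 = 2.9% to 1/18 = 5.6%

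**The case against.** The strongest defence is that the clause only separates subjects who passed entry from screen failures, whom SAP 7.2 reports separately. Protocol 9.2 forbids waivers, Protocol 13.5 restricts dispensing to subjects who met all entry criteria, and the schedules of assessments review eligibility at both Screening and Baseline. Neither document provides for judging eligibility again after dosing or for removing a dosed subject. Protocol 12.4.1 also builds its Safety population on enrolled subjects and does not define the word. The listing in SAP 7.5 is not tied to a population, so its unmet criteria could belong to screen failures. If 7.3 and 7.5 do expect violators among enrolled subjects, that suggests the authors never meant to exclude them.

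Most of this stands as evidence of intent. A reader might infer from the lead sentences that every dosed ineligible subject is certain to vanish from all main tables and that their adverse events are lost. The documents do not support that. The bullets for Cohort 1 and for Efficacy include such subjects. SAP 10.3 and 10.3.1 list all adverse events, with separate listings for deaths, serious events and discontinuations, and SAP 7.3 lists all deviations. Nor would the dose-escalation tables ordinarily be affected: Stage 1 and Stage 2 safety summaries are copied from the first interim report unless the underlying data have changed.

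The defence does not remove the conflict. A ban on waivers does not prevent errors discovered later. The bullets in 6.1.1 are introduced as members of a set that the lead sentence has already restricted. A programmer is left with two definitions and no rule for choosing between them.

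**Conclusion.** The point holds as an internal inconsistency in the population definitions that should be corrected before lock. Read literally, the stated rule would make membership of the safety set depend on eligibility, which is the wrong condition. Read with its bullets, the SAP mostly does not do this; the unresolved part is mainly Safety in Cohorts 2 to 4.

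The size is conditional. Neither document reports that an ineligible subject was dosed, so the effect may be zero. If there is one, it is about 8% to 25% of a cohort and about 3% to 6% of the study, on the planned sizes. The loss would fall on the summary tables from Stage 2 Period 5 onward. This assumes that the listings are produced as SAP 7.3 and 10.3 describe, without a population filter, and that the earlier-stage summaries are carried over unchanged.

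**What to change.** Change the SAP wording as follows.

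- **6.1.1:** in "completed the study entry procedures, and satisfied the eligibility criteria for the study, based on the inclusion and exclusion criteria", delete everything after the entry procedures. Define All Enrolled Subjects as all subjects who passed screening and entered a study stage in any cohort, whether or not an eligibility violation is found later. State that screen failures are excluded. Consent plus cohort assignment would not be a safe substitute: consent, subject numbering and system registration all occur at Screening, so screen failures could be swept in.
- **6.1.2:** define Safety as all subjects who received at least one dose of study medication, and make the Cohorts 2 to 4 bullet match.
- **6.1.3:** base Efficacy on the dosing and assessment conditions already in its bullets.
- **7.3 and 7.5:** report eligibility violations among enrolled subjects as flagged important deviations.

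The cost is wording only. No new data are needed, and SAP Section 2 allows changes until the SAP is finalised before database lock, expected on 24 July 2024. If no ineligible subject was dosed, no table changes.
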